Despite technological advances in the field of renal replacement therapy, mortality in haemodialysis (HD) patients remains high, comparable with cancer patients. The leading cause of death is cardiovascular disease. It is postulated that specific factors related to end stage renal disease play a detrimental role in increasing cardiac risk. One factor that has been identified is FGF-23, a molecule that increases with progressive renal dysfunction and causes uraemic cardiomyopathy in experimental models. FGF 23 levels remain high in HD patients receiving current standard dialysis treatment that removes largely small molecules. The new Baxter medium cut-off membrane (MCO, Theranova, Baxter Healthcare) has a higher molecular weight cut-off than conventional membranes that facilitates removal of larger i.e. medium-sized molecules. Studies on the new MCO membrane have reported increased exchange of beta 2 microglobulin (11.8kDa), myoglobin (17kDa), kappa free light chains (22.5kDa) complement factor D (24kDa), alpha 1 microglobulin (33kDa), YKL-40 (40kDa) and lambda free light chains (45kDa) (http://www.hdxtheranova.com/clinicaldata.html). However, there are no data on the impact of these membranes on FGF-23 (32kDa)

This study will investigate the difference in clearance of FGF-23 between MCO membranes and conventional dialysis membranes. It will also analyse the pattern of production, intradialytic removal and re-accumulation of FGF-23.

5 Aims of the proposed research

Primary Objective:

1. Comparison of FGF 23 clearance between conventional and medium cut off membranes.

Secondary Objectives:

- 1. Assessment of intra-subject stability of FGF 23 clearance
- 2. Examine rate of FGF 23 re-accumulation rate
- 3. Examine impact of type of membrane, phosphate, calcium and urea clearance and PTH levels on FGF-23 clearance

6 Study Design

This will be a prospective randomised case-crossover design study. This design helps mitigate confounding variables as each patient acts as their own control.

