Eligible participants will be stable haemodialysis patients on haemodialysis at Salford HD Unit and Bolton dialysis unit which is a satellite unit of Northern Care Alliance NHS Foundation Trust. Only patients who do not pass significant amount of urine (which indirectly indicates their own residual kidney function) and who have otherwise adequate dialysis treatment will be included (to allow comparison between different patients). Patients with active infection or cancer will not be included in the study as they are usually not in a steady state biochemical equilibrium to be able to assess impact of additional intervention.

Patients will be identified via electronic patient records (EPR) by the study coordinator and the research nurses from the Vascular Research Team (Research and Innovation Department, Northern Care Alliance NHS Foundation Trust). They will be approached by the research nurses and study coordinator during their routine vist for dialysis treatment and will be consented for entry into the study at their next routine appointment,. After informed consent, the patient will be randomly assigned to continue their dialysis treatments via either of the following two options via closed envelope.

Option 1: They will have one week of their usual thrice weekly dialysis treatment in a monitored fashion with traditional dialysis membrane. During this week, blood samples will be taken before and after dialysis via the dialysis circuits (without vene-puncture). Returned dialysate will also be collected and analyzed. Patients will then have three weeks of wash out period (when they will have their usual dialysis treatment). This will be followed by one week of monitored dialysis treatment with MCO dialysis membrane when again blood samples will be taken before and after dialysis and returned dialysate will be collected and analyzed.

Option 2: They will have one week of monitored dialysis treatment with MCO dialysis membrane. During this week, blood samples will be taken before and after dialysis via the dialysis circuits (without vene-puncture). Returned dialysate will also be collected and analyzed. This will be followed by three weeks of wash out period (when they will have their usual dialysis treatment). This will be followed by one week of monitored dialysis treatment with traditional dialysis membrane when again blood and dialysate samples will be taken.

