7.3 Study duration

Recruitment is expected to take about 6 weeks. After recruitment, the study itself will continue for five weeks in total; extendable to seven weeks in cases where wash out period needs to be extended due to acute illness. Last patient visit is expected to be after approximately 11 weeks. Processing of biological samples, statistical analysis and reporting of the results will be completed in 12 months.

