7.8 Withdrawal criteria

Participants will be allowed to withdraw from the study at any point. We will not collect any further data from this participant however will use data available during their time in the study for the final study analysis. If it is in the participant's best interest the clinician in charge of the study may also choose to withdraw the participant.

8 Regulatory and Ethical Considerations

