The re-accumulation rate of FGF 23 will be measured as (FGF23_{pre} – FGF 23 $_{post}$ previous HD session)/FGF-23_{post} previous HD session.

The average FGF 23 clearance values on conventional membranes will be compared with average values on medium cut-off membranes with paired-t test or Wilcoxon signed-rank test depending on the distribution of the data (irrespective of whether intra-subject stability is confirmed or not)

Further analysis will depend on the results of the intra-subject stability of FGF 23 clearance, that is, either it may be appropriate that the first HD session of each monitored session will be used for the analysis or each dialysis may need to be treated as separate event. In this case calcium, phosphate, URR, PTH, type of membrane and FGF -23 will be entered in a multiple linear regression analysis to determine relationships with FGF 23 clearance.

The data collected will be stored pseudo anonymised. A separate database with matched patient study code numbers will contain patient names, date of birth, hospital numbers and contact details. The data will be stored on the laptop computer and will be password protected with restricted access.

Power Calculation;

Sample size was calculated calculation was based on the recent study by Damasiewicz et al (6). If the log difference is 7.47 or greater, with 20 patients the study has a 80 % chance of detecting it at a two-sided 0.05 significance level.

11 Dissemination of Results and Publication Policy

Results will be presented in local/regional meetings and published in a journal. Results of the study will be publicised more widely via the Citizen Scientist initiative (see http://www.citizenscientist.org.uk/).

12 References

1. Suassuna PGA, de Paula RB, Sanders-Pinheiro H, Moe OW, Hu MC. Fibroblast growth factor 21 in chronic kidney disease. J Nephrol. 2018 Nov 14.

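### The primary paired test ignores the randomised membrane order; adjusting for period with a 10/10 envelope list would guard cheaply against any change between the two monitored weeks

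*Protocol*

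**What the plan says.** Section 6 describes the design in these words: "This will be a prospective randomised case-crossover design study". Each patient is "the patient will be randomly assigned to continue their dialysis treatments via either of the following two options via closed envelope": conventional membrane first or MCO membrane first. No allocation ratio or blocking is mentioned. Of the first option it says "Patients will then have three weeks of wash out period", and the second option has the same interval. Section 7.3 makes the study "extendable to seven weeks in cases where wash out period needs to be extended due to acute illness".

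The primary objective (section 5) is the comparison of FGF-23 clearance between membranes. Section 10 defines clearance per session as the pre-to-post fall divided by the pre-dialysis level. It averages clearance by membrane within patient, and the conventional-membrane averages "will be compared with average values on medium cut-off membranes with paired-t test or Wilcoxon signed-rank test depending on the distribution of the data". It names no period or sequence term there, and none among the covariates of the later multiple regression.

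On withdrawals, section 7.8 stops further collection but "will use data available during their time in the study for the final study analysis".

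**The concern.** Section 6 defends the crossover because patients serve as their own controls. That removes stable differences between patients. It does not remove changes over time within patients, such as a change in the assay, sample handling, the patient's condition or background treatment between the two weeks. Randomising the order is the design's protection against such changes, but the named analysis makes no use of the order.

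A period effect enters the difference MCO minus conventional with a plus sign in patients who have MCO second and a minus sign in those who have it first. The paired test treats this as patient-to-patient variation. With only 20 pairs, avoidable variation matters, and an uneven split leaves part of the shift in the estimate itself. Section 10 fixes this test for the primary comparison; it is not a detail left open for an analysis plan.

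**Working it through.** **Inputs.** From the documents: n = 20 (sections 7.1 and 10); two-sided alpha 0.05, 80% power and a log difference of 7.47 (section 10). Not given, hence assumed over a range: the SD of the paired difference, the period effect, the split between sequences, dropout, and the within-patient correlation.

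**The plan's own figure.** The stated 80% cannot be reproduced because no SD is given. A paired t-test with n = 20 (19 df) has 80% power at a standardised effect of 0.6604, which would imply an SD of 7.47/0.6604 = 11.31. Everything below is therefore in units of the SD of the paired difference, with the membrane effect set at 0.6604.

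**Model.** Let t be the membrane effect (MCO minus conventional) and p the period effect (second week minus first). Let n1 patients have conventional first and n2 have MCO first. The paired difference then has mean t + p in the first group and t - p in the second.

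- Mean of the paired differences: t + p(n1-n2)/n. The bias is p(n1-n2)/n, which is zero at 10/10.
- Expected sample variance at 10/10: 1 + p² × 20/19. For p = 0.25, 0.5 and 1 this is 1.066, 1.263 and 2.053.
- Period-adjusted estimate: half the difference between sequences in the mean of (second week minus first week). Its variance is (1/4)(1/n1 + 1/n2) on 18 df, whatever p is. The noncentrality is 2 × 0.6604/√(1/n1 + 1/n2): 2.95 at 10/10, 2.89 at 12/8 and 2.71 at 14/6.

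**Power at 10/10** (paired t by simulation, adjusted test by noncentral t):

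| Period effect (SD) | Paired t | Period-adjusted |
|---|---|---|
| 0 | 80.0% | 79.8% |
| 0.25 | 78.1% | 79.8% |
| 0.5 | 72.4% | 79.8% |
| 1.0 | 49% | 79.8% |

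The paired t-test is conservative here: its type I error is 3.0% at 0.5 SD and 0.6% at 1 SD.

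**Unequal sequences, period effect 0.5 SD:**

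| Split | Bias (SD) | Paired-t type I error, given that split |
|---|---|---|
| 12/8 | 0.20 × 0.5 = 0.10 | 4.5% |
| 13/7 | 0.30 × 0.5 = 0.15 | 6.7% |
| 14/6 | 0.40 × 0.5 = 0.20 | 9.8% |

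The bias can help or hurt. At 12/8, paired-t power is about 85% if the shift favours the membrane effect and about 57% if it opposes it; the adjusted test has 78.1% in both cases.

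**How likely is an uneven split?** If the envelopes were simple 1:1 randomisation (an assumption), Binomial(20, 0.5) gives 17.6% for exactly 10/10, 50% for 12/8 or worse, 26% for 13/7 or worse and 11.5% for 14/6 or worse. Averaged over that randomisation, the simulated type I error of the paired t-test was 5.1%, 4.9%, 5.1% and 5.0% for period effects of 0, 0.25, 0.5 and 1 SD.

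**Price of adjustment with no period effect.** Against 80.0% for the paired t-test, the adjusted test has 79.8% at 10/10, 78.1% at 12/8, 76.0% at 13/7 and 72.6% at 14/6. The losses are 0.2, 1.9, 4.0 and 7.4 points.

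**Patients with one monitored week.** They have no pair and cannot enter the paired test. Power of the paired test against a mixed model that includes their single week (within-patient correlation from 0.9 down to 0): 75.2% v 75.1–77.1% with 2 dropouts; 69.5% v 69.6–74.1% with 4. The gain is about 0 to 5 points, and nearly nothing when the correlation is high.

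**The case against.** The strongest reply is that no period effect is documented and the design limits one. Patients are stable, active infection and malignancy are excluded, the interval can be lengthened for acute illness, and the outcome is a within-session ratio. A 1 SD shift would be about 1.5 times the membrane effect for which the trial has nominal 80% power (1/0.66), and at 0.25 SD the loss is only about 2 points. This stands. The loss is conditional, and the larger figures show sensitivity rather than expectation.

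A reader might go further in several directions that the documents do not support:

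- *The test has an inflated type I error.* At 14/6 with a 1 SD shift the error is about 16%, but only given that split. Over simple randomisation it averages 5%, and at 10/10 it is below 5%.
- *Adjustment is nearly free.* The 0.2-point price holds only at 10/10. Averaged over unrestricted randomisation with no period effect, the adjusted test has 77.5% power against 80%.
- *Section 7.8 is contradicted.* It promises use of withdrawn patients' data in the final study analysis, without saying which one. The stability, re-accumulation and regression analyses could honour that promise. Only the primary comparison cannot use a single week.
- *The choice between t and Wilcoxon is itself the error.* The rule for that choice is commonly left to the analysis plan, which is not at hand.
- *The envelopes are unbalanced.* The protocol is silent on blocking, which often sits in a separate randomisation plan. Silence does not show that the list is unrestricted.

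**Conclusion.** The point holds in a conditional form. For a two-order randomised crossover, section 10 fixes a primary test that takes no account of order. If clearance changes between the monitored weeks, the test loses power at equal sequences (about 2, 8 and 31 points at 0.25, 0.5 and 1 SD) and becomes conservative. At unequal sequences, (n1-n2)/n of the change enters the membrane estimate in the realised trial. If there is no such change, nothing is lost.

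These figures rest on n = 20, roughly normal paired differences, an effect set to give exactly 80% power, and assumed period effects. The probabilities of uneven splits also assume simple 1:1 envelopes. This is a worthwhile improvement in efficiency and robustness, not a flaw that invalidates the comparison.

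**What to change.** Keep the clearance outcome as section 10 defines it, and make two changes together.

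1. Prepare the envelope list with 10 patients per order, and say so in section 6.
2. Make the primary comparison period-adjusted, in one of two pre-specified ways:
   - compare the within-patient period differences (second week minus first week) between the two sequences with a two-sample t-test on 18 df, and report half the difference in means with its 95% confidence interval; or
   - fit a linear mixed model with membrane and period as fixed effects, patient as random, and a small-sample correction to the degrees of freedom. This also lets patients with one monitored week contribute to the primary comparison, for a gain of 0 to 5 points of power.

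The cost is wording and an envelope list, with no extra patients, samples or visits. If there is no period effect, power falls by about 0.2 points at 10/10, about 2 at 12/8 and about 7 at 14/6. That is why the balanced list belongs with the adjustment. Withdrawals can still unbalance the sequences, and the adjusted estimate then remains free of the period shift.

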7.1 Recruitment procedure

We aim to recruit 20 patients for our study. Eligible study participants receiving regular HD at Salford and Bolton HD units will be identified by the study coordinator and the research nurses from the Vascular Research Team (Research and Innovation Department, Northern Care Alliance NHS Foundation Trust) from the electronic patient records. Patients will be approached by a member of the research team during their routine visit for dialysis treatment and will be provided written and verbal information about the study in a clinic room to ensure the privacy. Participants will have sufficient time (at least 24 hours) to consider their involvement in the study and consent may be taken at their next routine appointment by the research nurses or the study coordinator following .response to any relevant questions in a clinic room to ensure the privacy.

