8.5 Stopping rules

It is not anticipated that the study will be stopped prior to its intended end-date. However, the study will be halted if:

- New information comes to light which means that the aims of the study are futile.
- Safety issues come to light regarding the intervention.
- Resources to conduct the study are no longer available.

9 Record keeping and data management

- All outcome measures will be recorded on standardised data collection forms. These, together with the exclusion criteria screening proformas and consent forms, will all be stored in a secure area at the Vascular Research Team, Research and Innovation Department at Northern Care Alliance NHS Foundation Trust.
- Given this is a prospective data collection, the data will be pseudo anonymised before being stored. A separate database with matched patient study code numbers will contain patient names, date of birth, hospital numbers and contact details. The data will be stored on the NHS computer with following layers of security.
 - Patient data will only be saved on NHS computers.
 - NHS Computer will be located in secure NHS facility (swipe card/code protected entrance to the room) where only health care professionals are allowed to access.
 - \circ $\,$ Computers will be protected by start-up password.
 - Files will be password protected.
 - The PI, research nurses and study coordinators will have access to the data.
- Under the General Data Protection Regulation (GDPR), data will be anonymized, encrypted where necessary and access will be strictly restricted. Use of laptops and other portable devices will be avoided. Where it is necessary for them to be used, data will be encrypted and the data uploaded onto a secure server or desktop as soon as possible and the data removed from the portable device as soon as possible and using appropriate data destruction software. Under no circumstances, patients' or research participants" personal data will be stored on a home or other personal computer.

10 Statistical analyses and data handling

Statistical support has been provided by [name], Biostats Research Assistant (Research Assistant at University of Manchester.

The clearance of FGF 23 will be calculated as $(FGF23_{pre} - FGF 23_{post})/FGF 23_{pre}$ for each dialysis session and intra-subject stability will be assessed with repeated measures ANOVA or Friedman test, depending on the distribution of the data.

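### If sessions are analysed as separate events, the multiple linear regression for secondary objective 3 treats up to six correlated sessions per patient as independent, so its standard errors are wrong

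*Protocol*

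**What the plan says.** Secondary objective 3 (protocol section 5) is to "Examine impact of type of membrane, phosphate, calcium and urea clearance and PTH levels on FGF-23 clearance". Section 10 supplies the analysis. Clearance is computed "for each dialysis session and intra-subject stability will be assessed with repeated measures ANOVA or Friedman test", and what comes next depends on that stability result. One possibility is to use the first session of each monitored week. The other is that "each dialysis may need to be treated as separate event. In this case calcium, phosphate, URR, PTH" and the remaining terms go into one model: "type of membrane and FGF -23 will be entered in a multiple linear regression analysis to determine relationships with FGF 23 clearance". The section names no patient effect, period effect or variance correction for this regression.

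The number of rows follows from the design. Section 7.1 says "We aim to recruit 20 patients for our study". Section 6 gives each patient two monitored weeks, one per membrane, on a three-sessions-a-week schedule: "They will have one week of their usual thrice weekly dialysis treatment in a monitored fashion with traditional dialysis membrane" and, after the washout, "This will be followed by one week of monitored dialysis treatment with MCO dialysis membrane".

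The membrane comparison itself is handled separately in section 10, by a paired t-test or Wilcoxon signed-rank test on average clearance, whatever the stability test shows.

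**The concern.** Ordinary multiple linear regression assumes independent residuals. Repeated sessions of the same stable dialysis patient are unlikely to meet that assumption. The protocol recognises this elsewhere: it uses repeated-measures methods for stability and a paired test for the membranes, and it justifies the crossover in section 6 by saying "This design helps mitigate confounding variables as each patient acts as their own control". The regression as described drops that structure.

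The condition that leads into this branch does not repair it. Repeated measures ANOVA and the Friedman test ask whether the level of clearance shifts from session to session. Sessions can have equal means and be strongly correlated, or different means and be strongly correlated. Neither outcome licenses counting them as independent.

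At stake is the answer to secondary objective 3. A covariate that differs mainly between patients is informed by about 20 patients, but the regression would judge it as if 120 independent observations were available. A chance association of PTH, calcium, phosphate, URR or FGF-23 with clearance could then be reported as a predictor.

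**Working it through.** **Inputs from the protocol.** 20 patients (section 7.1); 3 sessions per monitored week and 2 monitored weeks (section 6). Rows per patient: 3 × 2 = 6. Total rows: 20 × 6 = 120.

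**Inputs assumed, because the protocol gives none.** Outcome intraclass correlation (ICC, the share of clearance variance lying between patients): 0.3, 0.5, 0.7. Between-patient share of each covariate's variance: 80%, varied from 50% to 95%.

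**The plan's own figure.** Section 10 states no figure for the regression. Its only calculation is 20 patients, 80% power, two-sided 0.05 and a log difference of 7.47 for detection. No SD is given, so it cannot be reproduced. Under a paired t-test it implies a standardised effect of 0.660 and an SD of differences of 7.47 / 0.660 ≈ 11.3. Nothing below depends on it.

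**Step 1: covariates constant within a patient.** Design effect = 1 + (6 − 1) × ICC; effective rows = 120 / design effect.

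- ICC 0.3: 1 + 5 × 0.3 = 2.5; 120 / 2.5 = 48
- ICC 0.5: 1 + 5 × 0.5 = 3.5; 120 / 3.5 ≈ 34
- ICC 0.7: 1 + 5 × 0.7 = 4.5; 120 / 4.5 ≈ 27

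**Step 2: simulation with covariates only partly constant.** 4,000 trials per setting, 20 patients × 6 sessions, ordinary least squares (OLS) on membrane and five covariates, no true effects, nominal 0.05, no patient-by-membrane variation. The two middle columns use the 80% share.

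| ICC | Covariate false-positive rate | Reported SE / true SE | Rate at 50% to 95% share |
|---|---|---|---|
| 0.3 | 0.18 | 0.68 | 0.13 to 0.23 |
| 0.5 | 0.26 | 0.57 | 0.18 to 0.31 |
| 0.7 | 0.33 | 0.50 | 0.23 to 0.39 |

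With ICC 0 and the 80% share, the rate is 0.05, so the inflation comes from the correlation and not from the number of covariates.

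**Step 3: membrane term.** Membrane varies within patients. Take total variance 1, patient share ρ and patient-by-membrane share δ, and ignore covariates.

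- True variance of the membrane difference: 2 × [δ + (1 − ρ − δ)/3] / 20
- OLS variance: about 4/120 = 1/30
- Reported SE / true SE ≈ 1 / √(1 − ρ + 2δ)

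The SE is therefore too large when δ is below ρ/2 and too small when δ is above it.

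| ρ | δ | Formula | Simulated, with covariates | Membrane false-positive rate |
|---|---|---|---|---|
| 0.3 | 0 | 1/√0.7 = 1.20 | 1.14 | 0.025 |
| 0.5 | 0 | 1/√0.5 = 1.41 | 1.30 | 0.014 |
| 0.7 | 0 | 1/√0.3 = 1.83 | 1.59 | 0.003 |
| 0.3 | 0.1 | 1/√0.9 = 1.05 | 1.01 | 0.049 |
| 0.3 | 0.3 | 1/√1.3 = 0.88 | 0.84 | 0.10 |
| 0.1 | 0.3 | 1/√1.5 = 0.82 | 0.79 | 0.12 |

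The simulated ratios are the relevant ones, because the planned model contains the covariates.

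**Step 4: primary test.** In the same simulations the paired t-test on patient averages had a false-positive rate of 0.04 to 0.05 in every setting.

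**The case against.** **The branch is conditional.** The protocol says sessions may need to be treated separately, not that they will be. This stands: the fault arises only if that branch is taken. The choice would, however, be made on a test that does not address independence.

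**Multiple linear regression does not exclude a patient term, and a SAP that is not shown could add one.** This is fair, but the protocol pairs that method with sessions as separate events. A mixed model in the SAP would depart from that description, so the wording is worth correcting.

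**The assumed correlations are not in the protocol.** This stands. For URR, excluding patients below 65% (section 7.2.1.b) may narrow the spread between patients. Even at a 50% between-patient share, the false-positive rate was 0.13 to 0.23.

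Three stronger readings are tempting and are not supported:

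- A reader might infer that the trial discards its pairing. It does not: the primary comparison is paired and is run irrespective of stability.
- A reader might infer that the membrane standard error is always overstated. That holds only when the membrane effect is similar across patients; step 3 shows the reversal.
- A reader might extend the fault to the first-session branch. The text most naturally ties the regression to the separate-event branch. If OLS were also run on two rows per patient, simulated rates would be 0.08 to 0.12 for covariates and 0.027 down to 0.002 for membrane, but the protocol does not say that it would be.

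**Conclusion.** The point holds, limited to secondary objective 3 and to the separate-event branch. There, the stated regression counts up to 120 correlated sessions from 20 patients as independent. For covariates that vary mostly between patients, the false-positive rate is about 15 to 35% at a nominal 5%, which is roughly three to seven times too high. For membrane type, the standard error is about 1.15 to 1.6 times too large if patients respond alike, and too small if the membrane effect varies strongly between them. These sizes rest on an assumed outcome ICC of 0.3 to 0.7 and on assumed covariate behaviour. The covariate inflation disappears if sessions of one patient are uncorrelated, which is implausible here. The primary conclusion about the membranes is not threatened.

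**What to change.** In section 10, replace the multiple linear regression with a linear mixed model on all sessions:

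- random patient and patient-by-membrane terms (the latter is the patient-week, since each membrane is used in one monitored week);
- fixed membrane and period;
- the covariates already listed;
- Kenward-Roger degrees of freedom.

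The patient-by-membrane term is needed. In simulations of the same 20 × 6 layout with a patient-by-membrane share of 0.3, a model with only a random patient intercept gave a membrane false-positive rate of about 0.19 to 0.26, against about 0.07 to 0.10 for OLS. An intercept-only model could therefore do worse than the method it replaces.

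At minimum, keep the regression but use patient-clustered standard errors with a small-sample correction.

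Keep the paired test as the membrane comparison, and remove the idea that the stability result decides whether sessions are independent. Label the covariate results exploratory, because only 20 patients inform the between-patient effects.

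The cost is a change of wording, slightly more analysis work and wider covariate intervals. No further patients, visits or samples are needed.

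### The power statement uses a log difference of 7.47, a scale the planned analysis does not use and a size unattainable in practice, so the stated 80% cannot be interpreted

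*Protocol*

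**What the plan says.** Section 7.1 sets the target: "We aim to recruit 20 patients for our study". The only support for that number is the power paragraph at the end of section 10: "If the log difference is 7.47 or greater, with 20 patients the study has a 80 % chance of detecting it", with the test taken "at a two-sided 0.05 significance level". The paragraph names one published study as its basis and cites it as reference (6). The list in section 12 has five entries, and that study is the fifth.

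Earlier in section 10 the outcome is defined: "The clearance of FGF 23 will be calculated as $(FGF23_{pre} - FGF 23_{post})/FGF 23_{pre}$ for each dialysis session". The clearance values are averaged for each membrane, and the conventional averages are then "compared with average values on medium cut-off membranes with paired-t test or Wilcoxon signed-rank test depending on the distribution of the data". Section 6 describes a randomised crossover in which patients serve as their own controls, so the data are paired. The protocol sets out no log-scale analysis of clearance and gives no SD for the within-patient difference.

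**The concern.** A power statement should give the difference that the planned test can detect, on the scale of that test. Here the test is on a fraction with an upper limit of 1, while the detectable effect is a logarithm-based figure more than seven times that limit. No variable is named to connect the two.

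At stake is the whole stated rationale for 20 patients. An ethics committee, funder or later reader cannot tell from the protocol what difference in FGF-23 clearance the trial was sized to find, or whether that difference would be worth finding.

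**Working it through.** **Inputs from the protocol.** Number of pairs n = 20 (sections 7.1 and 10); two-sided α = 0.05, power 80% and stated effect 7.47 (section 10, power paragraph); outcome (pre − post)/pre and paired test (section 10). Not given: log base, variable, SD of the paired difference.

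**1. Can the plan's figure be reproduced?** No. Without an SD the 80% cannot be recomputed. The calculation can only be run backwards, to find the SD that would make it true.

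**2. Standardised detectable difference.** For a paired t-test with n pairs, power = P(T > t(0.975, n − 1)), where T is noncentral t with n − 1 degrees of freedom and noncentrality d√n, and d is the mean paired difference divided by its SD. (The opposite tail is negligible here.) Solving for 80% power:
- n = 20: d = 0.660. The normal approximation gives (1.960 + 0.842)/√20 = 0.626. For the Wilcoxon test, with asymptotic relative efficiency 3/π, d is about 0.68.
- n = 18: d = 0.701.

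**3. SD implied by 7.47.** 7.47/0.660 = 11.3 (normal approximation: 7.47/0.626 = 11.9). With an SD of 5, power at 7.47 already exceeds 99.9%, so the 80% fits only an SD near 11.3 on whatever scale 7.47 is on.

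**4. Reading 7.47 as a log difference.**
- Base 2: 2^7.47 = 177-fold.
- Natural log: e^7.47 = 1,755-fold.
- Base 10: 10^7.47 = about 30-million-fold.

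**5. Reading 7.47 on the analysed scale.** Clearance on the medium cut-off membrane is at most 1. A difference of 7.47 therefore needs mean conventional clearance of at most 1 − 7.47 = −6.47. Since post/pre = 1 − clearance, mean post/pre would be at least 1 + 6.47 = 7.47. FGF-23 would have to rise to about 7.5 times its pre-dialysis level during conventional sessions, with complete removal on the other membrane.

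**6. What 20 pairs can detect on the analysed scale.** Detectable difference = d × SD. The SDs are assumptions, because the protocol gives none.

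| Assumed SD of paired difference in (pre − post)/pre | 20 complete pairs (0.660 × SD) | 18 complete pairs (0.701 × SD) |
|---|---|---|
| 0.05 | 0.033 | 0.035 |
| 0.10 | 0.066 | 0.070 |
| 0.20 | 0.132 | 0.140 |

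**The case against.** The strongest defence is that the label may be wrong rather than the calculation. If 7.47 meant percentage points of clearance, 80% power would need an SD of about 11.3 points, which is not absurd on its face. Power for 7.47 points would then be 89% at an SD of 10, 56% at 15 and 35% at 20. What stands is that no miscalculation has been demonstrated. But the protocol says log difference and gives no SD, so this reading is a guess and does not rescue the sentence.

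Several stronger conclusions are tempting, and the protocol does not support them:
- **That 7.47 is impossible.** The fraction has an upper limit of 1 but goes below 0 if FGF-23 rises during dialysis, so differences above 1 can occur in principle. Unattainable in practice is the accurate description.
- **That 20 patients is too few, or that the number is safe as it is.** Neither follows without an SD and a target difference.
- **That a null result could not be interpreted.** The observed paired difference and its confidence interval will show which effects are excluded, whatever the planning figure was.
- **That the cited study is unsuitable.** Its title concerns the stability and variability of FGF-23 levels in haemodialysis patients, which is a natural place to look for a variance. Its fitness for a difference in clearance cannot be judged from the title. The reference number is a clerical slip.
- **That lack of a withdrawal allowance is a serious fault.** Section 7.8 permits withdrawal, but at 0.66 SD the loss of two pairs lowers power only from 80% to 75%. Quoting the figure for 18 pairs is enough.

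**Conclusion.** The point holds as a fault of scale and size in a figure the protocol relies on, and not merely as detail that could be left to a statistical analysis plan. The effect is stated on a scale the planned test does not use. As a log difference it is at least 177-fold for the usual bases, and for 80% power it implies an SD of 11.3. The stated 80% therefore carries no usable information about the planned comparison.

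The 0.66 SD and 0.70 SD figures assume a paired t-test on approximately normal differences with complete pairs. The absolute differences rest on assumed SDs. The conclusion that 7.47 does not fit the analysis needs no assumed SD.

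**What to change.** In section 10, delete 7.47 and state the detectable difference on the scale that section already fixes, (pre − post)/pre. Suggested wording:

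*Twenty complete pairs give 80% power at a two-sided significance level of 0.05 to detect a mean within-patient difference in (pre − post)/pre of 0.66 SD of the paired differences (0.70 SD with 18 complete pairs).*

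The SD multiple is the same for any 20 pairs at these settings and justifies nothing alone. It should be converted to an absolute difference with a stated SD on the same scale and the source of that SD. A log(pre/post) version should not be offered as an alternative, since that would reopen the question of scale. If no SD on this scale is available, the protocol should say so and drop the claim of 80% power for any specific difference. The citation should be corrected from (6) to 5.

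The cost is one rewritten paragraph. The downside is that the stated power may become less favourable once it is tied to a real SD. Whether 20 patients still looks adequate can be judged only then.
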